11.5. Preexisting Condition

A preexisting condition, including abnormal physical exam findings, is one that is present at the start of the study and is to be recorded at the time of the Screening visit. A preexisting condition is only to be recorded as an adverse event if the frequency, intensity or the character of the condition worsens during study participation.

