5.4 Safety Variables

Assessment of the primary safety objective and other safety objectives will be performed on all subjects exposed to RBX2660 (Safety Population, see Section 6.3.1), and will include descriptive statistics. Additional sub-analyses of safety data may be performed on sub-populations.

5.4.1 *Primary Safety Endpoint*

Number of subjects with investigational product- and/or enema-related treatment-emergent adverse events (TEAEs).

5.4.2 *Other Safety Endpoints*

1. Number of adverse events per subject
2. Timing of attributable TEAEs
3. Duration of TEAEs
4. Relatedness of TEAEs
5. Severity of TEAEs
6. Causality of TEAEs to IP, enema, *C. difficile* or prior condition
7. Number of each of the following CDI-related TEAEs through 8-weeks post treatment: death, septic shock, toxic megacolon, colonic perforation, emergency colectomy, and intensive care unit (ICU) admission
8. Onset of new chronic conditions relative to treatment administration

5.4.3 *Adverse Events*

An adverse event (AE) is any untoward medical occurrence associated with the use of IP, whether or not the event is considered product-related. Preexisting conditions that worsen in frequency, intensity or character of the condition during study participation will be recorded as an AE. AEs will be recorded for each subject from the day of enrollment through the 6-month telephone assessment. Serious adverse events (SAEs) will be recorded for each subject from the day of enrollment through the duration of the study.

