6.6.2.5 Subject Diary including Solicited Adverse Events and Completion Compliance

All solicited adverse events recorded in the Subject Diary will be summarized utilizing frequencies (number of events), proportions (number of subjects with the event) and 95% CIs for categorical variables and using the descriptive statistics as listed in **Section 8.1** for continuous variables.

For each solicited event, severity scores will be summarized as both categorical and continuous values. For continuous summaries, severity scores will be identified as either pre-treatment or post-treatment (all diary entries captured after the first enema), and the average for each period will be calculated across individual subjects. Baseline for continuous summaries will be considered the average during the pre-treatment period. For categorical summaries, if a subject reports more than one severity score on the same date, the maximum severity will be used. Baseline for categorical summaries will be considered the last non-missing assessment prior to the enema.

For each categorical summary of event frequency, a two-sided 95% CI will be calculated using the normal approximation of the binomial.

The following summaries will be produced for the first enema:

- Frequency of severity scores on day of enema administration
- Frequency of severity scores on day 1 through 1-week post-treatment
- Frequency of maximum post-treatment severity score

Compliance in returning completed Subject Diaries will be calculated by dividing the number of diaries turned in, whether complete or not, by the number of diaries expected to be turned in. Furthermore, compliance will be summarized by calculating the proportion of subjects who turned in “complete” diaries, where complete is defined as answering all 14 daily questions (e.g.

11 solicited AE, Bristol Stool Type, New illnesses/injuries, New medications) for at least 80% of the expected number of diaries.

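### The categorical diary tables define a pre-enema Baseline that no listed output uses, so they cannot show how many subjects had new or worsened solicited symptoms

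*SAP*

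**What the plan says.** SAP 6.6.2.5 opens with "All solicited adverse events recorded in the Subject Diary will be summarized utilizing frequencies (number of events), proportions (number of subjects with the event"), and adds 95% CIs. For the first enema it lists three summaries: "Frequency of severity scores on day of enema administration", "Frequency of severity scores on day 1 through 1-week post-treatment" and "Frequency of maximum post-treatment severity score".

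It sets two pre-enema references. For categorical data, "Baseline for categorical summaries will be considered the last non-missing assessment prior to the enema". For continuous data, "Baseline for continuous summaries will be considered the average during the pre-treatment period"; continuous scores are labelled pre- or post-treatment and averaged within each period.

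The rules for recording an AE turn on worsening. Protocol 11.5 says "A preexisting condition is only to be recorded as an adverse event if the frequency, intensity or the character of the condition worsens", and SAP 5.4.3 says "Preexisting conditions that worsen in frequency, intensity or character of the condition during study participation will be recorded as an AE". Footnote 2 of the schedule of events (Protocol Table 10-1 and SAP 5.1) sends a diary symptom for AE assessment when its severity has risen relative to Screening.

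**The concern.** A categorical Baseline that is defined and then left out of every listed categorical output looks like an omission. Without it, a subject whose bloating was moderate before the enema and moderate after it falls in the same cell as one whose moderate bloating began after the enema.

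Such background symptoms are plausible. The symptom-control condition in Protocol 7.3.1 concerns loose-stool counts only. IBD is not an exclusion criterion and is a planned safety subgroup (SAP 6.6.2.6), and IBS is among the comorbidities recorded (Protocol 16). Gas, bloating, cramping or nausea can therefore be present at the last pre-enema entry.

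With no control group to show the background rate, a reader of the diary tables cannot tell how much of what is reported followed treatment and how much was already there. That matters for a study whose primary objective is safety and tolerability, even though these tables only supplement the main safety analysis.

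**Working it through.** The plan states no rate, sample size or power on this point, so there is no figure to reproduce. The check is a comparison of the text, followed by an illustration on assumed inputs.

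**Step 1. Where each reference is used in SAP 6.6.2.5**

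| Summary | Pre-enema reference | Listed output that uses it | Shows number worsened? |
|---|---|---|---|
| Event counts, subject proportions | None stated | None | No |
| Categorical severity (three outputs) | Last non-missing pre-enema entry | None | No |
| Continuous severity | Pre-treatment average | Separate pre and post averages | No |

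The data exist: the diary is kept daily from Screening to the day before the enema, for up to 21 days (Protocol 10.3), and through day 7 after it (SAP 5.4.4.1).

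**Step 2. Why the averages do not fill the gap.** If k subjects rise by one grade and k fall by one grade, the mean change is (k − k)/N = 0 whatever k is. The means allow a before/after comparison for the group but do not give the number who worsened.

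**Step 3. Possible size.** All rates here are assumptions. Let

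- b = share with the symptom at the last pre-enema entry;
- u = share of those whose maximum post-enema grade is above zero but not above Baseline;
- v = share of those whose maximum exceeds Baseline;
- n = share of symptom-free subjects with new onset.

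Then:

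- any post-enema symptom = b(u + v) + (1 − b)n
- new or worsened = bv + (1 − b)n
- gap = bu, which involves neither v nor n.

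With v = 0, N = 750 (the cap on treated subjects) and 95% CI = p ± 1.96√(p(1 − p)/750):

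| Case | b, u, n | Any symptom (95% CI) | New or worsened (95% CI) | Gap = b × u |
|---|---|---|---|---|
| Low | 10%, 50%, 10% | 0.05 + 0.09 = 14.0% (11.5–16.5) | 9.0% (7.0–11.0) | 5 points |
| Middle | 30%, 80%, 10% | 0.24 + 0.07 = 31.0% (27.7–34.3) | 7.0% (5.2–8.8) | 24 points |
| High | 50%, 80%, 5% | 0.40 + 0.025 = 42.5% (39.0–46.0) | 2.5% (1.4–3.6) | 40 points |

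Setting v = 0 excludes worsening in subjects who already had the symptom. Take the opposite extreme in the middle case: the remaining 20% (1 − 0.80) all worsen. Any symptom becomes 0.30 × 1.00 + 0.07 = 37%, and new or worsened becomes 0.30 × 0.20 + 0.07 = 13%. The gap is still 24 points, but subjects not above Baseline fall from 24/31 = 77% to 24/37 = 65% of those counted.

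**Step 4. Comparators.** Three references are in play: Screening (footnote 2), the last pre-enema entry (categorical) and the pre-treatment average (continuous). The same diary can be classed as worsened under one and not under another.

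**The case against.** The strongest reply is that the main safety analysis already covers this. Footnote 2 routes symptoms that rise from Screening to the investigator. Those recorded as AEs enter the TEAE tables by SOC and PT, severity, relatedness and onset interval. The primary endpoint counts subjects with related TEAEs. Solicited events are not among the endpoints in SAP 5.4.2; they sit under other observations in SAP 5.4.4. All of this stands, and it confines the point to the diary tables.

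Three stronger readings are tempting, and the documents do not support them.

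- A reader might infer that the plan never compares diary scores with the pre-enema period. It does: the same section defines both baselines and averages pre- and post-treatment scores separately.
- A reader might infer that every diary symptom is counted as an adverse event. The SAP does not say which score makes an entry an event, and the three listed outputs are distributions of scores. The missing threshold is a gap in definition, not proof of that rule.
- A reader might take the 51.5% (17/33) reporting solicited events on Day 7 in the first Phase 2 study (Protocol 5.3.1) as evidence of common background symptoms. It is a post-dose figure from another study and does not measure pre-enema prevalence.

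Increased diarrhea is relative by name, and Protocol Table 11-1 grades it as stools over baseline. That weakens the point for one of the 11 events. In the same table, gas, bloating, cramping and chills are graded by interference with activities, with no baseline term.

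A shift table also has a fair objection against it. A maximum over about a week set against a single entry will show apparent worsening from day-to-day variation alone. If the diary is complete, that single entry falls in the 24–72 hour antibiotic washout. The fix has to allow for this.

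**Conclusion.** The point holds in a limited form. The categorical Baseline in SAP 6.6.2.5 is used by none of the three listed categorical outputs, and the pre/post means cannot give the number of subjects who worsened. In a single-arm study the solicited-event tables therefore cannot separate unchanged pre-existing symptoms from new or worsened ones.

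The size is unknown. The range of 5 to 40 percentage points rests wholly on assumed prevalence (10% to 50%) and persistence (50% to 80%), and should be read only as showing that the gap could be small or large.

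It would be wrong to conclude that the primary endpoint or the TEAE tables are inflated: they rest on investigator-recorded AEs under the worsening rules. In the diary tables, the risk is that background symptoms are read as post-treatment ones, not that harm is hidden. This is a worthwhile reporting correction at little cost, not a flaw in the main safety analysis.

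**What to change.** In SAP 6.6.2.5:

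1. For each of the 11 solicited events, add a shift table of Baseline severity (last non-missing pre-enema entry, as already defined) by maximum post-enema severity. Report n (%) and 95% CI of subjects above Baseline.
2. Add a sensitivity version that compares the post-enema maximum with the maximum over a pre-enema window of similar length.
3. Call the result *new or worsened solicited symptoms*. Avoid *treatment-emergent*, because SAP 5.4.3.4 defines TEAEs by onset date.
4. Keep the absolute tables, labelled *diary symptoms (any)*, and state which score makes a diary entry an event.
5. Reconcile the comparator with footnote 2 of the schedule, which uses Screening.

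The cost is SAP wording, one or two extra tables and a footnote for subjects without a pre-enema entry. Some subjects will have a pre-enema diary shorter than a week, so the sensitivity version should state how they are handled. No new data are needed.

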6.6.2.6 Subgroup safety analysis

The overview of AEs and TEAEs by SOC and PT will be summarized by the following subgroups:

- Subjects with immunocompromising conditions;
- Subject without immunocompromising conditions;
- Subjects with inflammatory bowel disease at time of IP administration;
- Subject without inflammatory bowel disease at time of IP administration.

Note: Inflammatory bowel disease includes the medical history with PT term “Ulcerative colitis”, “Crohn's disease”, or “Inflammatory bowel disease”.

6.7 Efficacy Analysis

6.7.1 *Analyses Supporting the Efficacy Endpoints*

6.7.1.1 Treatment Success

Assessment of secondary efficacy objectives will include descriptive statistics and will be performed on the mITT population. Additional sub-analyses of safety data may be performed on sub-populations.

6.7.1.1.1 Recurrence of CDI within 8 weeks of treatment

Recurrence of CDI is defined as the presence of CDI diarrhea within 8 weeks (54-60 days) of administration of a study enema, which includes a positive stool test for *C. difficile* as determined by the central laboratory. A CDI with an onset after 8 weeks (> 60 days) from completion of the study treatment is considered a new CDI. Onset of CDI is the date that the symptoms first started.

The efficacy parameter used to determine treatment success is defined as the absence of CDI diarrhea through 8 weeks after completing a study treatment. Efficacy assessments will occur at each scheduled contact: 1-week, 4-weeks, 8-weeks.

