7.3.6. Treatment Failure

Treatment failure (CDI recurrence) is defined as:

- The presence of CDI diarrhea within 8 weeks of administration of a study enema, which includes a positive stool test for *C. difficile* as determined by the central laboratory.

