12.3. Assessment of Efficacy, Secondary Objectives

Assessment of secondary objectives will include descriptive statistics and be performed on pre-defined analysis populations including Intent-to-Treat (ITT), modified Intent-to-Treat (mITT) and Per-Protocol (PP). Additional sub-analyses of safety data may be performed on sub-populations.

Secondary Efficacy Endpoints:

1. Recurrence of CDI within 8 weeks of treatment.

Recurrence of CDI after 8 weeks from completion of the study treatment is considered a new CDI.

The efficacy parameter used to determine treatment success is defined as the absence of CDI diarrhea through 8 weeks after completing a study treatment. Efficacy assessments will occur at each scheduled contact: 1-, 4- and 8-weeks.

2. Loss of sustained clinical response through 6 months after treatment

Sustained clinical response is defined as treatment success of the presenting CDI recurrence and no new CDI episodes through 6 months after completing a study treatment. Efficacy assessments will occur at each scheduled contact: 4 and 6 months.

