the Baseline visit (enema administration) and it will be collected and reviewed at the 1-week follow-up visit.

Subjects may receive a second RBX2660 enema if they are deemed failures following treatment per the protocol-specified treatment failure definition. This second enema is to be administered within 21 calendar days of failure determination. If a subject receives a second RBX2660 enema, the follow-up is completed via telephone assessments at 1-week, 4-week, 8-weeks, and 6-months after completing the second enema. A final analysis and report will be completed once the last subject has completed the 6-month follow-up visit for their study treatment, including 6-month follow-up after a second RBX2660 study treatment, if applicable.

3.1.1 ***Treatment Success***

Treatment success is defined as:

- The absence of CDI diarrhea through 8 weeks after completing a study treatment.

3.1.2 ***Sustained Clinical Response***

Sustained clinical response is defined as:

- Treatment success of the presenting CDI recurrence and no new CDI episodes through 6 months after completing a study treatment.

3.1.3 ***Treatment Failure***

Treatment failure (CDI recurrence) is defined as:

- The presence of CDI diarrhea within 8 weeks of administration of a study enema, which includes a positive stool test for *C. difficile* as determined by the central laboratory.

To ensure consistency across clinical sites for the determination of study failure, the central laboratory will perform the required C. DIFF QUIK CHEK COMPLETE® Test (QCC Test) rapid enzyme immunoassay test for glutamate dehydrogenase (GDH) and toxins A and B.

In the case of suspected treatment failure where there is an immediate concern for subject safety, including the potential for serious adverse events, a test may be conducted at the site or other laboratory known to the site **in addition to** sending a sample to the central laboratory for testing. In the event, the test results from the central laboratory differ from that of a local laboratory, the results from the central laboratory will be used in determination of treatment failure and eligibility to receive a second treatment with RBX2660.

3.1.4 ***Definition of Indeterminate Treatment Outcome***

If neither the protocol-specified definition for Treatment Success nor Treatment Failure is met, the treatment outcome will be considered Indeterminate.

3.1.5 ***Determination of Treatment Outcome***

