The site investigator will make the initial determination of treatment success or failure based on the protocol-defined study definitions. The site investigator's assessment will then be provided to the Endpoint Adjudication Committee for independent adjudication of treatment success or failure that will be utilized for study analysis and reporting purposes. This may be done in an ongoing basis or a single meeting. Details of the EAC logistics, activity and responsibilities will be included in an EAC charter.

3.2 **Blinding**

This study is not blinded.

3.3 **Determination of Sample Size**

The purpose of this study is to assess the safety and tolerability of RBX2660 in a recurrent CDI population that is broader and more inclusive than that included in prior studies using RBX2660. In order to continue to collect prospective safety information and allow open-label treatment access to a broader population of patients, up to 750 subjects will be treated with RBX2660. As an open-label study, there are no statistical powering considerations for the revised sample size.

Subjects who have signed informed consent forms but do not meet all eligibility criteria will be considered screen failures. Subjects who withdraw for any reason prior to administration of the enema will be replaced without counting toward the sample size treatment cap of 750 subjects.

3.4 **Treatment**

Active treatment consists of one dose of RBX2660 delivered via enema.

4 **CHANGES IN THE CONDUCT OF THE STUDY OR PLANNED ANALYSES**

4.1 **Changes in the Conduct of the Study**

There have been no changes to the conduct of the study or planned analysis, however, ad hoc analyses may be performed as needed to support regulatory review.

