1. **Efficacy Endpoint:** Recurrence of CDI within 8 weeks of treatment.

Recurrence of CDI after 8 weeks from completion of the study treatment is considered a new *C. difficile* infection.

The efficacy parameter used to determine treatment success is defined as the absence of CDI diarrhea through 8 weeks after completing a study treatment. Efficacy assessments will occur at each scheduled office visit: 1-, 4- and 8-weeks.

2. **Efficacy Endpoint:** Loss of sustained clinical response through 6 months after treatment

Sustained clinical response is defined as treatment success of the presenting CDI recurrence and no new CDI episodes through 6 months after completing a study treatment. Efficacy assessments will occur at each scheduled phone assessment: 4 and 6 months.

5.6 **Other Endpoints**

Other endpoints include the following:

1. Baseline characteristics: sex, age, number of prior CDI events, race, ethnicity
2. Subject fecal microbial composition at Screening, 1-week, 4-weeks, 8-weeks, 4 months, and 6 months after study treatment
3. Cdif32 questionnaire at Screening, 1-week, 8-weeks, 4 months, and 6 months

4. Recurrence of CDI within 8 weeks of a second RBX2660 treatment
5. Concentration of vancomycin resistant enterococcus in stool samples for subjects who were carriers at Baseline at 1-week, 4-weeks, 8-weeks, 4 months, and 6 months after study treatment.
6. Presence of *C. difficile* in stool samples at Screening, 1-week, 4-weeks, 8-weeks, 4 months, and 6 months after study treatment

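### SAP 6.7.1.1.1 uses the 8-week visit window (days 54-60) as the limit for a recurrence dated by symptom onset, while the protocol and the rest of the SAP use 8 weeks with no tolerance

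*SAP*

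**What the plan says.** SAP 6.7.1.1.1 gives the analysis rule for the first secondary endpoint in three sentences:

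- The recurrence rule is: "Recurrence of CDI is defined as the presence of CDI diarrhea within 8 weeks (54-60 days) of administration of a study enema", with a positive central laboratory test.
- The rule for a new infection is: "A CDI with an onset after 8 weeks (> 60 days) from completion of the study treatment is considered a new CDI".
- The event is dated by symptoms and not by the visit: "Onset of CDI is the date that the symptoms first started".

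The next paragraph of the same section defines treatment success as no CDI diarrhea through 8 weeks, with no day range.

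The other definitions also carry no tolerance:

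- Protocol 7.3.6, treatment failure: "The presence of CDI diarrhea within 8 weeks of administration of a study enema". SAP 3.1.3 repeats it: "The presence of CDI diarrhea within 8 weeks of administration of a study enema, which includes a positive stool test".
- Protocol 7.3.7 and SAP 3.1.1 define success through 8 weeks.
- Protocol 12.3, new infection: "Recurrence of CDI after 8 weeks from completion of the study treatment is considered a new CDI". SAP 5.5.1 has the same sentence.

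The range 54-60 appears elsewhere only in SAP Table 1, as the window for the 8-week office visit. In Protocol Table 10-1 the ± 3 days governs the timing of visits and calls. SAP 4.1 reports no departure: "There have been no changes to the conduct of the study or planned analysis".

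**The concern.** A visit window allows for late or early attendance. An event dated by first symptoms needs no such allowance, because a visit on day 60 can still record an onset on day 50. Using the window as the event limit moves the boundary between recurrence and new CDI, and no passage says that this was intended or why.

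An onset just after 8 weeks then satisfies two incompatible definitions, and within 6.7.1.1.1 itself it meets both the recurrence rule and the success rule. A programmer cannot implement the section without choosing between them. At stake is the 8-week recurrence or success rate, the first secondary endpoint. The same failure definition also governs access to a second enema (Protocol 7.5), and Protocol 10.13 ties assessment of possible failure to suspected recurrence within 8 weeks. A subject could therefore be a failure in the analysis but not under the protocol.

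**Working it through.** **Step 1: reproduce the SAP's range.** SAP 5.2.1 makes the enema date relative day 1. Eight weeks is 8 × 7 = 56 elapsed days, which is relative day 56 + 1 = 57. Then 57 ± 3 = 54 to 60, exactly the Table 1 window for the 8-week office visit.

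**Step 2: find the disputed days.** With no tolerance, the last recurrence day is relative day 57. SAP 6.7.1.1.1 does not say which scale its 60 is on.

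- If 60 is a relative day, the disputed onsets are days 58, 59 and 60: 3 days.
- If 60 is elapsed days, it equals relative day 61, and the disputed onsets are days 58 to 61: 4 days.

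**Step 3: classify an onset on relative day 59.**

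| Passage | Classification |
|---|---|
| SAP 6.7.1.1.1, first paragraph | recurrence |
| SAP 6.7.1.1.1, second paragraph | treatment success |
| Protocol 7.3.6, 7.3.7 and SAP 3.1.1, 3.1.3 | not a failure; treatment success |
| Protocol 12.3 and SAP 5.5.1 | new CDI |

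**Step 4: size the effect.** Inputs from Protocol 5.3.4 (prior Phase 3 study, RBX2660 group) are 70.4% success at 8 weeks and sustained response in 116 of 126, so 10 of 126 successes were lost later. Up to 750 subjects are treated (Protocol 12.1). Days 58-181 span 124 days. How the late losses fall over time is assumed, since the documents do not report it.

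- Even spread, 3 days: (10/126)/124 × 3 × 0.704 = 0.135 percentage points; × 750 = 1.0 subject.
- Even spread, 4 days: 0.180 points; 1.35 subjects.
- Only half of the 10 were CDI onsets, 3 days: 0.068 points; 0.5 subject. The protocol does not say that all 10 were dated CDI onsets.
- Half of the losses in the first 30 days, 3 days: (0.5 × 10/126)/30 × 3 × 0.704 = 0.279 points; 2.1 subjects.
- Deliberately high case, in which the average hazard of weeks 0-8 persists: λ = −ln(0.704)/56 = 0.00627 per day, and the shift is 0.704 × (1 − exp(−λk)). For k = 3 this is 1.31 points, 9.8 subjects; for k = 4, 1.74 points, 13.1 subjects.

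**Step 5: sustained response.** A subject with onset on a disputed day loses sustained response under either rule, so the rate over all treated stays at 0.704 × 116/126 = 64.8%. If it is reported among 8-week successes, only the denominator moves. With 750 × 0.704 = 528 successes and 486.1 sustained, the rate is 486.1/528 = 92.1%, against 486.1/(528 − 1.01) = 92.2% (even spread) or 486.1/(528 − 2.10) = 92.4% (front-loaded).

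**Separate one-day slips in the windows.**

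- Protocol 7.2 allows treatment up to 21 days after screening. By the SAP 5.2.1 formula, such a screening visit is day −21. Table 1 starts at −20 and SAP 6.3 says 20 days, so a compliant visit can fall outside its analysis window.
- Table 2 schedules days 121 and 181, but 121 ± 14 = 107-135 and 181 ± 14 = 167-195. The printed 106-134 and 166-194 equal 120 ± 14 and 180 ± 14. SAP 6.6.2.1 uses days 120 and 180; Table 3 uses 121 and 180+.

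**The case against.** The best defence is that the SAP is turning 8 weeks into days. The protocol gives no day number for failure, and it assesses outcome at a visit with a ± 3 day window. Protocol 5.3.3 shows a similar practice in an earlier study, where follow-up of at least 56 days was read as days 49-63. On this view no change needed declaring in SAP 4.1. The precedent is weak, because that range concerned evaluability and not the date of an event. The defence also leaves the second paragraph of 6.7.1.1.1 in conflict with the first. What stands is that the range may be a clarification badly worded, not a rule knowingly altered.

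Four stronger readings are tempting and are not supported:

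- *The adjudication committee and the analysts will apply different limits.* Protocol 7.4 and SAP 3.1.5 tie the study definitions to the investigator's initial determination and leave the committee's working details to a charter that is not among the documents. The charter may already fix the day. A conflict is possible but not shown.
- *SAP Table 3, which closes 0-8 weeks at day 57, is a rival efficacy rule.* It concerns adverse-event onset, and Protocol 11.1 excludes a recurrence from adverse events unless it requires hospitalization of at least 24 hours.
- *Only onsets on days 54-60 count.* The following sentence, with its limit beyond 60 days, shows that an upper bound is meant.
- *The wider limit flatters the product.* It adds failures.

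It is also fair that Protocol 7.3.6 turns on the presence of CDI diarrhea, which needs two consecutive days of symptoms and a positive test, and not on first symptom alone. The limit must therefore say which date it applies to.

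**Conclusion.** The inconsistency is real and lies in the text: the 8-week visit window has become the boundary for an onset-dated event in one SAP passage, against the protocol and the SAP's other definitions. Onsets on relative days 58-60, or 58-61, are classified two ways.

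The size is small. About 1 of 750 subjects (0.14-0.18 points) would move on the even-spread assumption, and 0.5 to 2 of 750 under the other two assumptions for a 3-day extension. The 10-13 of the persistent-hazard case is a high bound and not an expectation. All these figures borrow the prior Phase 3 rates and an assumed timing of late losses. The endpoint is secondary and descriptive, the study is unpowered, and the primary safety endpoint is untouched. The case for acting rests on an ambiguous pre-specified definition that is cheap to correct, not on a likely change in conclusions.

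**What to change.** For analysis, state the boundary between recurrence and new CDI once, as a single day number on a named scale (relative or elapsed), counted from the relevant enema, applied to a named date, and consistent with the protocol's 8 weeks. Use it in SAP 3.1, 5.5.1 and 6.7.1.1.1 and in the adjudication charter. Keep 54-60 only as the visit window in Table 1. If a tolerance is intended, declare it with its reason in SAP 4.1.

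The wording must also be reconciled with Protocol 7.5 and 10.13, which use the same failure definition for the second enema and the suspected-recurrence visit. No clinical rule is proposed here.

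As separate editorial corrections, let the Screening window and SAP 6.3 cover the full 21 days the protocol allows (day −21 by the SAP formula). Put the 4- and 6-month scheduled days, their windows, the Table 3 limits and the days in SAP 6.6.2.1 on one convention.

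The cost is a few lines of SAP text and a matching line in the charter, with no change to data collection.
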